### **5.3 Methods of Minimizing Bias**

Excluded bias in our collective

- No selected participants
- Both sexes can be included
- Any age

Potential bias in our collective:

- Since we will search for healthy volunteers, the microbiome analysis might be slightly different to the population undergoing a hip arthroplasty surgery in an orthopedic hospital.

## **6 STUDY POPULATION**

Ten healthy male and female volunteers'  $\geq 18$  years in each arm will be recruited for this clinical study.

### **6.1 Eligibility Criteria**

#### **6.1.1 Inclusion Criteria**

Patients fulfilling all of the following inclusion criteria may be enrolled in the study

Inclusion criteria:

Healthy male and female participants  $\geq 18$  years who

- volunteer for the pilot study in which PDT will be applied and effect of skin colonization will be analyzed, and
- an informed consent is signed by the participant (after information about the project).

#### **6.1.2 Exclusion Criteria**

The presence of any one of the following exclusion criteria will lead to exclusion of the participant:

Exclusion criteria:

- Pregnant and lacting women
- Participants inability to follow the procedures of the study, e.g. due to language problems, psychological disorders, dementia, etc.,
- Participants taking antibiotics in the 14 days prior to PDT or until follow-up at 14 days
- Participants who received oral retinoid therapy within the last 6 months
- Participants who received anti-inflammatory agents as NSAR within the 14 days prior and after the PDT
- Photodermatoses Participants taking any photosensitizing drugs within 4 weeks prior to PDT
- Fitzpatrick's skin phototype V-VI

## 6.2 Recruitment and Screening

Volunteers for this pilot study will be recruited by the Division of Infectious Diseases of the University Hospital Zurich with a flyer (appendix 2) as a recruitment tool (on pinboard at the University Hospital Zurich and the University Hospital Balgrist). Written informed consent will be taken under supervision of PD Dr. [name].

The participants will be informed in writing and verbal on:

- The nature, purpose and duration of, and procedure for the research project;
- Their right to withhold or to revoke their consent at any time without giving reasons;
- Their right to receive information at any time in response to further questions relating to the research project;
- Their right to be informed of results concerning their health, and their right for such information or to designate a person who is to take this decision for them;
- Measures to protect the biological material and the personal data

All participants will have enough time to decide whether to participate or not (at least 1 week). The formal consent of a participant will be obtained before the participant is submitted to any study procedure. The consent form will be signed and dated by the investigator or his designee at the same time as the participant sign. A copy of the signed informed consent will be given to the study participant. The form will be retained as part of the study records in the patient file.

There will be a financial compensation (value CHF 50.00) to the participants.

## 6.3 Criteria for Withdrawal/ Discontinuation of Participants

A participant must be withdrawn from the study if

- safety reasons of PDT (other side effects than expected, or more intense known side effects).
- Withdrawal of participant informed consent

[figure not shown]
Participants who discontinued the study (premature withdrawal) will be follow-up at least once after PDT treatment (1 week) to ask for side effects. If no intervention was done, no follow-up is needed.

After withdrawal of consent, the encoded patient samples and data will be analyzed. After analysis, the samples and data will be completely anonymised (according to Art. 9 KlinV), except if the participant has consented to further use of the samples and data and not withdrawn his consent. In this case, the samples and data will be stored as mentioned in chapter 12.6."

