Inclusion / Exclusion criteria:	
Inclusion criteria  Healthy male and female participants <math>\geq 18</math> years who
 
 
volunteer for the pilot study in which a routine photodynamic treatment in the Department of Dermatology will be applied and effect of skin colonization will be analyzed, and
 
an informed consent is signed by the participant (after information about the project).
 
 
Exclusion criteria
 
 
Pregnant and lacting women
 
Participants with inability to follow the procedures of the study, e.g. due to language problems, psychological disorders, dementia, etc.,
 
Participants taking antibiotics in the 14 days prior to PDT or until follow-up at 21 days
 
Participants who received oral retinoid therapy within the last 6 months
 
Participants who received anti-inflammatory agents as NSAR within the 14 days prior and after the PDT
 
Participants taking any photosensitizing drugs within 4 weeks prior to PDT
 
Participants who had a history of photosensitivity disorder
 
Fitzpatrick's skin phototype V-VI
 

Study Intervention:	
 
Photosensitizer application, followed by PDT (1x)
 
Skin swabs on day 0, 1, 3, and 5
 
 
Group A: use of MAL induced Pp IX photosensitizer  Group B: use of Methylene blue photosensitizer

Reference Intervention:	Skin swabs before and after skin antisepsis in 10 participants without PDT from the contralateral side.
Number of Participants with Rationale:	Aim: 10 volunteers in group A and 10 volunteers in group B There will be only descriptive statistics to see if numbers of colonizing bacteria are decreased with PDT to plan a clinical trial in patients getting a hip joint arthroplasty and previous antisepsis.
Study Duration:	1 year
Study Schedule:	
 
Project start (FPFV): January 2021 
 
First participant: January 2021
 
Last participant: June 2021
 
 
 
Project end (LPLV): December 2021
 

Investigator(s):	[name] Division of Infectious Diseases and Hospital Hygiene University Hospital Zurich [name] Email: [contact] [contact]
Study Centre(s):	Single-center

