### **4.3 Safety Outcomes**

Every PDT is documented as in routine clinics on a standardized protocol in the KISIM database (see appendix 1).

Clinical signs and symptoms after PDT as adverse events. We will distinguish between:

- Mild redness and pain as to be expected (yes/no)
- Advanced redness and pain more than expected (yes/no): adverse event.
  - o “More than expected” is defined, if patients needs to take more than 1 painkiller/day
- Other signs and symptoms not expected (yes/no)

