## **5 STUDY DESIGN AND COURSE OF STUDY**

### **5.1 General Study Design and Justification of the Design**

This is a pilot study of healthy volunteers, open label, and single center. We will use a parallel assignment of Arm A and B without masking (open label). Allocation is non-randomized, we will start with group A, followed by group B.

If we see promising results, we will plan a prospective clinical trial in patients undergoing hip arthroplasty surgery.

[figure not shown]
The intended procedures are PDT on the first day followed by skin swabbing for control of skin microbiome of treated area immediately after PDT (day 0) and after 1, 3 and 5 days of PDT to analyze how long the effect lasts.

We think that this study design with healthy volunteers is adequate before starting a clinical trial.

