### **7.4 Data Collection and Follow-up for Withdrawn Participants**

Not applicable

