### **8.2.4 Assessments in Participants who prematurely Stop the Study**

Participants who are withdrawn from the study prematurely due to adverse event, will be followed-up until adverse-effects disappeared. Follow up may include but is not limited to physical examination, laboratory tests, vital signs, telephone calls. Outcomes and resolution of events will be recorded in the Case Report Forms. In case of lost to follow up, efforts will be made to contact the patient or to ascertain the vital status of the participant.

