### 10.4 Handling of Missing Data and Drop-Outs

Missing outcome data will be handled as missing. No imputation methods will be used.

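### Section 6.3 requires withdrawal from the study for stronger reactions to a single PDT session, and nothing provides for the later primary-outcome cultures in those participants

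*Combined protocol and SAP*

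**What the plan says.** The synopsis lists the intervention as "Photosensitizer application, followed by PDT (1x)", and section 7.2.1 repeats that it is a single application. Section 5.1 explains the later sampling: swabs are taken "after 1, 3 and 5 days of PDT to analyze how long the effect lasts". Section 8.2.1 sets the primary outcome, bacterial density and species, at visits 1 to 4, that is days 0, 1, 3 and 5.

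Section 6.3 opens with "A participant must be withdrawn from the study if" and gives as its first ground "safety reasons of PDT (other side effects than expected, or more intense known side effects)". For premature withdrawals after PDT it then asks for at least one contact, at 1 week, about side effects.

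Section 7.4, on data collection and follow-up for withdrawn participants, says only "Not applicable". Section 8.2.4 says "Participants who are withdrawn from the study prematurely due to adverse event, will be followed-up until adverse-effects disappeared". It allows physical examination, laboratory tests and telephone calls among other means, and has the outcome recorded in the case report form.

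Section 10.3.1 defines the analysis set as participants who terminated the study. Section 10.4 says "Missing outcome data will be handled as missing", with no imputation.

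**The concern.** With a single session, withdrawal after the session cannot reduce exposure to PDT. It does end the scheduled assessments. The rule is mandatory, applies to the study and not only to treatment, and is triggered by the intensity or unexpectedness of the skin reaction.

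Reaction intensity is not incidental here. Section 3.2 says the project needs the photosensitizer with the best balance between antibacterial effect and skin irritation. Section 2.4 makes the larger study depend on sterile cultures without side effects. Under the plan as written, one half of that balance (irritation) decides who stops contributing data on the other half (the day 1 to 5 cultures). If one photosensitizer irritates more, its group loses more cultures, and the two groups are then described on differently selected participants. Samples that were never taken cannot be recovered by widening the analysis set.

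**Working it through.** **1. What each section provides after a safety withdrawal**

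| Section | Side effects | Day 1, 3, 5 cultures |
|---|---|---|
| 6.3 | At least one contact at 1 week | Not mentioned |
| 7.4 | Declared not applicable | Declared not applicable |
| 8.2.4 | Until resolved, no fixed days | Not mentioned |
| 9.4 | Ongoing SAEs, and AEs of laboratory values or vital signs | Not mentioned |

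Two things follow. Section 7.4 contradicts 6.3 and 8.2.4 on side effects. No section keeps the cultures.

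**2. The trigger and the analysis set are also open**

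- Section 4.3 gives a threshold for a reaction that is more than expected: it "is defined, if patients needs to take more than 1 painkiller/day". Section 6.3 does not refer to it, so the number who would meet the withdrawal rule is not determined.
- Section 10.3.1 rests on the word terminated. Section 9.4 uses terminating for both regular and premature ends, so it is unclear whether withdrawn participants are analysed at all.
- Section 7.5 limits the analysis to participants without antibiotics or NSAR until 14 days. A strong reactor who takes an NSAR for pain could be removed by that route too.

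**3. How likely is a loss?**

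The documents give no withdrawal rate, so a rate q of 5% to 30% is assumed. With 10 per group:

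- P(at least 1 lost) = 1 − (1 − q)^10
- P(at least 2 lost) = 1 − (1 − q)^10 − 10q(1 − q)^9

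| q | At least 1 of 10 | At least 2 of 10 |
|---|---|---|
| 5% | 40% | 9% |
| 10% | 65% | 26% |
| 20% | 89% | 62% |
| 30% | 97% | 85% |

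**4. What a loss does to the culture result**

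The sample size of 20 (section 10.2) is an aim without a calculation, so there is no planned precision to reproduce. Take sterile or not sterile as a simple summary and suppose every remaining participant is sterile. The exact two-sided 95% lower limit for n out of n is 0.025^(1/n). If k of 10 are not sampled, the full-group sterile share lies between (10 − k)/10 and 1.

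| k withdrawn | Observed | Lower limit | Full-group share |
|---|---|---|---|
| 0 | 10/10 | 0.025^(1/10) = 69.2% | 100% |
| 1 | 9/9 | 0.025^(1/9) = 66.4% | 90–100% |
| 2 | 8/8 | 0.025^(1/8) = 63.1% | 80–100% |
| 3 | 7/7 | 0.025^(1/7) = 59.0% | 70–100% |

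The fall in the lower limit reflects only the smaller n. The range in the last column is what selective loss adds.

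**5. Direction**

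Assume 20% withdrawn and 60% of milder reactors colonised on a later day.

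- Strong reactors at 90%: true share 0.2 × 0.90 + 0.8 × 0.60 = 66%, against 60% observed, so 6 points too low.
- Strong reactors at 30%: true share 0.2 × 0.30 + 0.8 × 0.60 = 54%, against 60% observed, so 6 points too high.

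The documents give no basis for choosing between these.

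**The case against.** The other side has several good points.

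- **Skin observation does not stop.** A reader might infer from 7.4 that nothing more is collected and that redness on later days is understated. The documents do not support this. Section 8.2.4 requires follow-up until the effects resolve, recorded in the case report form, and 6.3 adds a contact later than day 5. Only the fixed-day timing is not assured.
- **Strong reactors are not absent from the data.** A reader might infer that the time course covers milder reactors only. A withdrawn participant still contributes the day 0 baseline and every sample taken before withdrawal. Section 6.3 says samples and data are analysed even after consent is withdrawn, and 10.3.1 can be read to include these participants.
- **Withdrawal may protect the skin.** Sections 8.1 and 8.3.3 schedule antisepsis, with scraping before and after it, at each later visit. Scraping is done with a scalpel and the antiseptic is a povidone-iodine/alcohol solution. Ending these procedures on reacting skin may be deliberate.
- **The number may be small or zero.** Section 2.6 expects less erythema than in the earlier pilot, 4.3 treats mild redness and pain as expected, and the analysis is described as descriptive.

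All four stand, and they narrow the point. They do not supply the missing cultures: no section says whether primary-outcome sampling continues after a 6.3 safety event.

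**Conclusion.** The point holds in a limited form. Following the plan as written loses later primary-outcome cultures selectively by reaction intensity, and perhaps unevenly between the groups. Section 7.4 contradicts 6.3 and 8.2.4.

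The size depends on a withdrawal rate that the documents do not give; with no withdrawals there is no effect. With 2 of 10 withdrawn and the rest sterile, the full-group sterile share can be stated only as 80–100%. A reader might also infer that the loss flatters or penalises PDT, for example because reaction and bacterial killing might rise together. The documents do not establish that link, and the direction stays open.

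This should be corrected before enrolment. No view is taken on when a participant should be withdrawn for safety.

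**What to change.** Reconcile 6.3, 7.4, 8.2.4 and 10.3.1, leaving the clinical safety rule to the investigators.

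- **7.4:** replace the present entry with a data-collection rule. After a safety event, the already scheduled day 1, 3 and 5 skin assessments and cultures are still collected where the participant consents and the investigator judges the procedures, both scraping and antisepsis, acceptable. Record the reason for any sample not taken.
- **6.3 and 8.2.4:** align the 1-week contact and the follow-up to resolution with that rule, and distinguish withdrawal of consent from a safety event.
- **10.3.1:** state that these participants remain in the analysis set, and check this against 7.5.
- **Reporting:** give results by day, with the number sampled and their reaction category.

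The cost is protocol wording; section 8.1 already schedules these visits for every participant. The small downside is that a few people with stronger reactions are asked to attend visits they would otherwise skip.

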# 7 STUDY INTERVENTION

## 7.1 General Information

The following flowchart shows all steps described in the study plan:

### 7.1.1 Study Intervention

#### Study Intervention(s) (group A and B)

Who	List of interventions
PD Dr. med. [name]	Skin antisepsis, taking swabs, PDT with MAL (group A) or Methylene blue (group B)

\* In collaboration with Dr. med. [name] from the Department of dermatology and [name] (emeritus Professor of the University of Zurich, group leader of oral oncology).

### 7.1.2 Control Intervention

Skin antisepsis without PDT on the contralateral site of the first 10 participants

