## 2.5 Explanation for Choice of Comparator Intervention

We will use for our control group without PDT the contralateral groin of the same participants (no further participants needed).

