## 2.7 Study Population

Twenty healthy male and female volunteers'  $\geq 18$  years will be recruited for this clinical study. The first ten enrolled participants will be allocated to receive MAL (group A), the other ten participants will receive Methylene blue (group B). The type of PDT (group A and B) is not blinded to both participant and study investigator. The study will be approved by the local ethical committee and conducted with a study nurse and a doctoral thesis student (to be determined) in collaboration with the Clinic for Dermatology at the University Hospital Zurich, and with the Institute of Medical Microbiology at the University of Zurich. An informed consent will be obtained from each participant. We will exclude pregnant and lactating women, participants taking antibiotics in the 14 days prior to the PDT or until follow-up at 21 days, participants who received oral retinoid therapy within the last 6 months, participants who received anti-inflammatory agents within the 14 days prior and after the photodynamic treatment, participants taking any photosensitizing drugs within 4 weeks prior to the photodynamic treatment, participants who had a history of photosensitivity disorder or having a Fitzpatrick's skin phototype V-V (16).

We will not include vulnerable participants. There will be a financial compensation (value CHF 50.00) to the participants as in the previous trial (PHOMIC) was asked by the ethical committee.

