## **5.2 Study Duration and Study Schedule**

The expected duration of participant's participation is 6 days from first study visit to the last follow-up time to report side effects of photodynamic treatment. The screening visit can be any time before but at least 1 week before the first study visit. The study schedule is indicated below.

**Figure 1.** Flow chart of the study\*

\*Visit 2 must be within 24 hours after photodynamic treatment

\*\* same participants as in the PDT group but swabs and skin antisepsis on the contralateral leg site

At the screening visit, the voluntary participant will be informed and asked for signing the informed consent by [name]. This visit and the last visit will be at the outpatient clinic for Infectious Diseases at the University Hospital Zurich. Demographic data (age, sex, current medications, and underlying diseases) will be noted.

Appointments for the photodynamic treatment (day 0) and the control visits (day 1, 3 and 5) will be made.

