#### Group B (Methylene blue group)

On day 0, a skin scraping of the groin will be performed and sent for microbiological culture. Then, 5ml of the 0.01% methylene blue based photosensitizer (NF-031) will be applied for an area of 5 x 10cm in the right groin of the patient. Immediately after application, the photodynamic process will be started by irradiation of the area with 40J/cm^2 red light from a 635nm (absorption peak 670nm) emitting LED during 4 minutes.

Immediately after the PDT, skin antisepsis will be performed. Antisepsis of the skin is performed with a povidone-iodine/alcohol solution (Betaseptic®, Mundipharma, Limburg, Germany) and repeated three times for a total duration of 3 minutes to imitate standard surgical antisepsis before a hip arthroplasty surgery. Skin scraping will be repeated after the antisepsis and after 1, 3 and 5 days for bacterial cultures.

As a control group, we will take skin swabs before and after skin antisepsis without PDT on the contralateral site of all participants.

On day 5 of the study, volunteers will be seen for the last study visit to document any adverse effects.

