## 7.2 Administration of Study Intervention

### 7.2.1 Study Intervention

Since the clinic of dermatology is located in the circle and not anymore in the main campus of the University Hospital of Zurich, the study intervention on day 0 is at the circle.

The following visits can be done at the main campus at the department of Infectious Diseases.

Details of study Intervention	Justification
1. Inguinal skin scraping before PDT	Baseline microbiome data
2. Photosensitizer application, followed by PDT (1x)	Treatment to reduce colonization bacteria
3. Skin scraping, skin antisepsis in the groin, skin scraping after antisepsis	To measure bacterial colonization after PDT – before and after skin antisepsis

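### Section 7.1.2 limits the no-PDT control groin to the first 10 participants, all of them group A; Section 5.2 takes it from everyone, so 7.1.2 followed literally leaves methylene blue without a same-person comparator

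*Combined protocol and SAP*

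**What the plan says.** The control is described in five places, and they do not agree.

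- Section 7.1.2, which defines the control intervention: "Skin antisepsis without PDT on the contralateral site of the first 10 participants".
- Synopsis, Reference Intervention: "Skin swabs before and after skin antisepsis in 10 participants without PDT from the contralateral side". It does not say which ten.
- Section 5.2, study schedule: "As a control group, we will take skin swabs before and after skin antisepsis without PDT on the contralateral site of all participants".
- Section 5.2, footnote to Figure 1: "same participants as in the PDT group but swabs and skin antisepsis on the contralateral leg site". It sets no limit on number or arm.
- Section 2.5 uses the other groin of the same people as the control, also without a limit.

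The order of enrolment is fixed. Section 2.7: "The first ten enrolled participants will be allocated to receive MAL (group A), the other ten participants will receive Methylene blue (group B"). Section 5.1: "Allocation is non-randomized, we will start with group A, followed by group B".

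The day-0 visit instructions in Section 8.3.2 do not mention the control groin, so they do not settle the matter.

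**The concern.** The two instructions cannot both be carried out. Because enrolment is sequential, the limit in 7.1.2 removes the control from one whole arm.

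The hypothesis in Section 10.1 is that PDT improves skin antisepsis. Testing that idea, even descriptively, means setting the result after PDT plus antisepsis beside the result after antisepsis alone. The untreated groin of the same person is the comparator that Section 2.5 chose. Section 2.4 makes sterile cultures after both steps, without side effects, the condition for planning a larger study. In group B such a culture would have no antisepsis-alone result from the same person beside it. The only such results would come from group A: other people, sampled earlier, with no randomization to make the two groups comparable.

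Methylene blue is the photosensitizer that the preceding pilot, as described in Section 2.1, did not test. A day-0 control swab that is missed cannot be taken later.

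**Working it through.** **Inputs.** Arm sizes are 10 and 10 (synopsis, Section 6), and the total is 20 (Section 10.2): 10 + 10 = 20, which agrees. The plan gives no effect size, rate or power, so there is no sample-size calculation to reproduce. The check is a count.

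**Control groins by arm.** Participants 1–10 are group A and 11–20 are group B (Sections 2.7 and 5.1).

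| Wording followed | Group A | Group B | Total |
|---|---|---|---|
| 7.1.2 (first 10) | 10 | 0 | 10 |
| 5.2 (all) | 10 | 10 | 20 |
| Synopsis alone (10, unspecified) | 0–10 | 0–10 | 10 |

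**Control scrapings on day 0**, two per control groin (before and after antisepsis): 2 × 10 = 20 under 7.1.2 and 2 × 20 = 40 under 5.2. The difference is 20.

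**What group B keeps under 7.1.2.** It keeps its scraping before PDT. Section 7.2.1 also lists, after PDT, "Skin scraping, skin antisepsis in the groin, skin scraping after antisepsis", and the table in 8.1 agrees. On that schedule the change directly after PDT stays visible, and the before/after description in 10.3.2 can still be done. The narratives in 5.2 and 8.3.2 do not mention a scraping between PDT and antisepsis. If staff follow those, PDT and antisepsis effects in group B cannot be separated from its own data at all.

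**What the missing control would hide.** The documents give no groin sterility rate for antisepsis alone, so the rates here are assumptions. Suppose all 10 in group B are sterile after PDT plus antisepsis, and antisepsis alone sterilises a proportion p. The added benefit is 10 − 10p:

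- p = 0.3: 10 − 3 = 7 of 10
- p = 0.7: 10 − 7 = 3 of 10
- p = 0.9: 10 − 9 = 1 of 10

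Without control groins in group B, the arm's own data look the same in all three cases.

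**Share of total sampling**, counting control swabs on day 0 only:

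- Under 7.2.1 and 8.1, the treated groin has 3 scrapings on day 0 and 2 at each of 3 later visits: 3 + 6 = 9, and 9 × 20 = 180. The total is 180 + 20 = 200 under 7.1.2 and 180 + 40 = 220 under 5.2, so 20/200 = 10% more.
- Under 5.2, the treated groin has 1 before PDT, 1 after antisepsis and 3 later: 5 × 20 = 100. The totals are 120 and 140, so 20/120 = 17% more.

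**The case against.** The best case against is that nothing planned is lost. Section 10.3.2 describes data before and after PDT, Section 10.3 calls the analysis descriptive only, and no part of Section 10 names a comparison of treated with control groin. The condition in Section 2.4 is absolute and can be judged in group B without a control. Ten reference groins could be a deliberate choice for a pilot, and two places say ten. Since each arm has exactly ten people, the phrase in 7.1.2 may be loose wording for ten per arm. The figures that are not shown might make the intention clear.

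The ten group A controls would also remain as an outside reference. With 10 of 10 sterile in group B and 3, 7 or 9 of 10 sterile among those controls, two-sided Fisher p is about 0.003, 0.21 and 1.0. Exact McNemar with group B's own controls would give about 0.016, 0.25 and 1.0. The reading at the 0.05 level is the same in each case, provided the two groups are exchangeable.

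Some of this stands. The before/after analysis survives, Section 10 does not use the control in either arm, and the loss is not one of statistical power. What does not stand is the proviso: the arms are filled one after the other without randomization, so exchangeability is exactly what cannot be assumed. Section 7.1.2 does not say ten per arm, and Section 2.7 uses almost the same words for group A. No drawing can remove a conflict between two sentences of text. The absolute condition in 2.4 does not answer the hypothesis in 10.1, which is about improvement over antisepsis.

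**Conclusion.** The concern holds. Section 7.1.2 contradicts Section 5.2. Section 2.5 and the Figure 1 footnote side with 5.2, while the synopsis gives 7.1.2's number without naming the ten. Read literally, 7.1.2 gives 10 control groins in group A and 0 in group B, against 10 and 10 under 5.2.

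The loss is specific: no within-participant comparison of PDT plus antisepsis with antisepsis alone for methylene blue. The before/after description is unaffected. The counts rest only on the stated enrolment order and arm sizes. The 7, 3 and 1 of 10 illustration rests on assumed sterility rates and on treating the culture as simply sterile or not, whereas Section 8.2.1 grades growth semiquantitatively. This should be corrected before group B starts, because the missing swabs could not be recovered.

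**What to change.** Reword Section 7.1.2 and the Reference Intervention entry in the synopsis to match 5.2: a day-0 control in the untreated groin, with swabs before and after antisepsis and no PDT, in all 20 participants. Section 10.3.2 should then name the descriptive comparison of treated with control groin within each arm; otherwise the control data have no stated use.

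Separately, Sections 5.2, 8.1 and 8.3.3 need to be reconciled on whether antisepsis is repeated at follow-up and on whether the last sampling is day 5 or day 7. The protocol should also state which follow-up procedures, if any, apply to the control groin. If that groin does not follow the treated groin's schedule, conclusions about PDT against control should be limited to day 0.

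Compared with 7.1.2, the cost is 20 extra day-0 scrapings, or 60 agar plates at the three per sample in Section 8.2.1 (20 × 3), plus freezing and any PCR on those samples. Each of ten group B volunteers has one antisepsis of the untreated groin, a second scraped site and a longer day-0 visit, all of which 5.2 already foresees. No extra visits, participants or follow-up control swabs are needed.
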